Directions for taking height: Have subjects remove their shoes before taking their height. Height should be recorded to the nearest 1/2 inch (for example 60.5").

Directions for taking blood pressure: Have subjects sit for 5 minutes before taking blood pressure.

WITHDRAWAL PROCEDURES: If at any time during the study, the subject decides to withdraw consent they will be referred back to their Primary Care Manager (PCM). If a subject is found to be diabetic during the course of the study, they will be withdrawn and referred to their PCM to initiate standard of care treatment. Standard of care typically follows the DoD Clinical Practice guidelines for self-monitoring of blood glucose. As part of this, the Air Force provides glucometers and supplies at no charge.

ADVERSE EVENTS (AEs) AND DEVIATIONS: The Associate Investigator (AI) at each site is responsible for reviewing, categorizing, and properly reporting to the main PI AEs that occur with their subjects. The "Algorithm for Determining Whether an Adverse Event is an Unanticipated Problem" is attached to assist in guiding the research staff on the categorizing of Adverse Events, Protocol Deviations, and Serious Adverse Events.

Serious Adverse Events (SAEs) and Serious Protocol Deviations are defined as unexpected events that increase the risk to subjects and that were possibly, probably, or definitely related to the research. These must be reported to the WHASC IRB within 5 days. Each site is responsible for reporting these to [name], the local Site Principal Investigator, and [name] immediately via the "Possible Internal (Local) Reportable Unanticipated Problem Involving Risk to Subjects or Others (UPIRSO)" form.

If a subject experiences an allergic reaction during the study, they will be instructed to stop taking the study medication and seek urgent medical treatment.

Adverse Events (AEs) and Protocol Deviations that do not increase the risks to subjects like those listed in the "risks" section of this protocol are to be reported to [name], the local Site Associate Investigator and [name] as they occur or no later than the 1st workday of every month via the "WHASC Tracking Log for Adverse Events (AEs)/Protocol Deviations Not Requiring Immediate Reporting. This is done to ensure ongoing monitoring and identification of trends that may arise.

Guidance for completing the SAE/AE forms:

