- When completing the forms, please ensure that you include as much information as possible, to include:
 - o Date the patient reported the event
 - o Date the event occurred or the date that you discovered the event happened/began
 - o A detailed description of the event including any tests/procedures that were performed with dates
 - o Any directions given to the patient including the date
 - o Description of the resolution with the date
- When answering the questions:
 - o "Was the event unexpected?": Select YES only if the event was NOT already listed in the risks/benefits section of the Protocol or part of an existing disease process.
 - o "Did the event cause increased risk to participants or others?": Select YES only if the adverse event was serious, which includes events that are life threatening or results in: death, inpatient hospitalization, prolongation of existing hospitalization, persistent or significant disability/incapacity, congenital anomaly/birth defect, or may jeopardize the subject's health and may require medical or surgical intervention to prevent one of the outcomes above. If the event is not serious but there is a trend that would warrant a change in the protocol/ICD (i.e. several patients experienced a rash), then you would also select YES.
 - o "Was the event possibly, probably, or definitely related to the research procedures?": Select YES if it is due to the research itself not underlying disease or disorder. If there isn't adequate information available to assess this, the answer would be NO.

- o "Should the consent form/process be revised": Select YES only if it warrants a revision to the research process or risks/benefits (this should be discussed with [name] if you are selecting YES).
- o "Summary of events in the opinion of the local investigator": please have your Local Site Associate Investigator comment such as "no increased risks to subjects participating in the study" (just an example). Then have your Site Associate Investigator sign, print their name, and date. Then return the scanned copy to [name] and [name]. They will then get the Research Monitor to complete Section 6, and return a copy to be filed in the subjects file.

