4.4. Assent Process: N/A

4.5. Benefits:

The benefits to the subjects may include lower hemoglobin A1c levels and improvement of long-term health by decreasing the risk of developing diabetes.

4.6. Risks:

Risks to the subject are minimal as the subjects have been diagnosed with pre-diabetes and will have to be treated regardless if they participate in this study or not. There are no known risks associated with water-soluble cinnamon, as it is a compound granted GRAS (Generally Recognized as Safe) status by the United States Food and Drug Administration. Potential risks include the inadvertent disclosure of personal health information and a potential for a cinnamon allergy that is not already known by the subject. The risks associated with the blood draw include bleeding, feeling light-headed, and bruising at the blood draw site and infection. Risks and side effects related to the water-soluble cinnamon extract include those, which are:

Less likely and not serious:

- **Hypoglycemia (low blood sugar):**
 - Heart palpitations (abnormal heart beats either fast or slow)
 - Tremors (involuntary muscle movement)
 - Hunger
 - Sweating

*If a subject experiences any of these symptoms, they are instructed to eat 15-20 grams of sugar [for example glucose (sugar) tablets], a glass of juice or other snack containing sugar, and then eat some carbohydrates (for example a small meal or cracker with peanut butter).

Less Likely and serious

- **Cinnamon and Wheat Bran:** There may be a risk that the subject has an allergy to cinnamon and wheat bran that they are not aware of currently. The signs and symptoms of an allergic reaction include:
 - o Shortness of breath
 - o Hives (itchy rash)
 - o Runny nose
 - o Watery eyes
 - o Sore eyes
 - o Asthma
 - o Lip swelling
 - o Tongue swelling
 - o Nausea
 - o Brochospasm (a bronchial spasm is a sudden constriction of the muscles in the walls of the bronchioles)
 - o Anaphylaxis (whole-body allergic reaction that has the following signs and symptoms):
 - Abdominal pain or cramping
 - Abnormal (high-pitched) breathing sounds
 - Anxiety
 - Confusion
 - Cough
 - Diarrhea
 - Difficulty breathing
 - Difficulty swallowing
 - Fainting, light-headedness, dizziness
 - Hives
 - Itchiness
 - Nasal congestion
 - Nausea, vomiting
 - Palpitations
 - Skin redness
 - Slurred speech
 - Wheezing

*If the subject experiences any of these symptoms, they are instructed to stop taking the study medication and seek urgent medical treatment.

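### A related, life-threatening allergic reaction in either arm falls outside the protocol's SAE definition and has no stated IRB deadline

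*Combined protocol and SAP*

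**What the plan says.** Section 3.6, under adverse events and deviations, gives the document's only SAE definition: "Serious Adverse Events (SAEs) and Serious Protocol Deviations are defined as unexpected events that increase the risk to subjects". It adds a third condition, that the event is at least possibly related to the research. Events that meet all three conditions go to the IRB within 5 days. The other route is a tracking log, sent to study staff and the site Associate Investigator as events occur or by the first workday of the month. Its scope, worded by reference to the risks section, begins "Adverse Events (AEs) and Protocol Deviations that do not increase the risks to subjects like those listed in the". Its title says that it is for events that need no immediate reporting.

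The form guidance that follows puts the same three conditions as yes/no questions.

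- Unexpected: "Select YES only if the event was NOT already listed in the risks/benefits section of the Protocol". An event that belongs to an existing disease is also answered no.
- Increased risk: yes only for a serious event, described by outcome, such as one that is "life threatening or results in: death, inpatient hospitalization, prolongation of existing hospitalization". There is one extension, also answered yes: "If the event is not serious but there is a trend that would warrant a change in the protocol/ICD".
- Related: yes if the research itself, not the underlying disease, is the cause; no if there is too little information to judge.

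Section 4.6 places allergy among the less likely but serious risks: "There may be a risk that the subject has an allergy to cinnamon and wheat bran that they are not aware of currently". Its list of signs ends with "Anaphylaxis (whole-body allergic reaction that has the following signs and symptoms". Hypoglycemia is listed separately as not serious. The blood-draw risks (bleeding, light-headedness, bruising, infection) are listed with no grade of severity.

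**The concern.** Whether an event is serious should depend on its outcome. Under Section 3.6 it also depends on whether the risks section foresaw the event. A harm that Section 4.6 itself calls serious can then never be recorded as a serious adverse event.

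Two things are at stake. One is the expedited IRB report, which is tied to the SAE label. The other is the meaning of any safety statement. Section 3.6.1 sets out to assess the safety of long-term use, and the first monitoring objective in Section 4.9.5 names SAE reporting. A report of no SAEs would naturally be read as no serious events, and under this definition it would not mean that.

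**Working it through.** The plan gives no figure to reproduce. The check applies the three questions in Section 3.6 to specific events. All three answers must be yes for an SAE.

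| Event | Unexpected? | Increased risk? | Related? | SAE with 5-day report? |
|---|---|---|---|---|
| Life-threatening anaphylaxis caused by cinnamon | No (listed as serious) | Yes | Yes | No |
| Life-threatening anaphylaxis caused by the wheat bran placebo | No (listed as serious) | Yes | Yes | No |
| Hospitalization for related hypoglycemia | No if the name alone counts as listed; yes if the severity must match | Yes | Yes | Depends on the reading |
| Hospitalization for infection at the blood-draw site | As above | Yes | Yes | Depends on the reading |
| Unlisted, related, life-threatening event | Yes | Yes | Yes | Yes |
| Unlisted, related, non-serious trend that warrants a protocol change | Yes | Yes (trend rule) | Yes | Yes |
| Unrelated hospitalization | Either | Yes | No | No |

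The first two rows do not depend on how the word listed is read, because anaphylaxis is named and graded serious. The sixth row shows the definition failing in the other direction.

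Next, does other text supply an IRB deadline for the first two rows?

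1. Tracking log. If its scope is events that do not increase risk, a life-threatening reaction does not belong there, and neither route fits. If the comparison with listed risks brings it in, the log names study staff and the site investigator as recipients and sets no IRB deadline.
2. Section 4.9.1. Issues go at once to an investigator. The IRB is not mentioned.
3. Section 4.9.5. It commits to Good Clinical Practice in general terms and states no deadline.
4. The algorithm cited in Section 3.6 (Section 13, item 15). It is not reproduced, so its content is unknown.

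Last, timing. Product stops at Visit 5, and Visits 6 to 9 follow at 90-day intervals: 4 × 90 = 360 days. If the last subject finishes by 30 April 2018 (Section 3.6.4 ends in April 2018), that subject stopped product about 5 May 2017. This is 264 days before the document date of 24 January 2018. With 80-day intervals, 4 × 80 = 320 days, the stop date is 14 June 2017 and the gap is 224 days.

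**The case against.** The strongest reply is that this passage is an unanticipated-problem screen carrying the wrong name. The form it prescribes is titled for unanticipated problems, the attached algorithm concerns them, and the three questions suit that purpose. This explains how the wording arose and points to the remedy. It does not cure the rule, because the sentence defines SAEs and attaches the 5-day report to that definition.

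A second reply is that the algorithm is meant to guide how staff categorize events and may handle this case. That cannot be excluded. The finding is limited to the text available. A helpful attachment would still conflict with the protocol's own definition.

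A third reply concerns breadth. A reader might infer that every harm listed in Section 4.6 is excluded however severe. The documents do not support that. The guidance does not say whether an event is listed by name or at a given severity. Hypoglycemia is listed only as not serious, and the blood-draw harms carry no serious outcome. The guidance's own example of a trend is a rash, although Section 4.6 lists hives and explains them as an itchy rash, so the authors may not have intended mechanical matching. This objection stands for those two groups. It does not reach serious allergic reactions.

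Finally, there is real oversight: the site investigator signs the event form, the Research Monitor completes a section of it, and Section 4.9.5 names a primary and an alternate monitor. None of this sets an IRB deadline.

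**Conclusion.** The point holds for serious allergic reactions in both arms. As written, a related, life-threatening one is not an SAE and has no IRB deadline in the available text. For a serious outcome of hypoglycemia or of a blood draw, the same follows only on a literal, name-only reading.

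The size is a matter of classification and does not depend on event rates. The number of events affected is not in the documents and could be 0, in which case only the wording changes. If the April 2018 end date holds, new reactions to the product can arise only in subjects who restarted it, though blood draws continue to Visit 9. The main gain is then correct classification of events already logged.

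Three further inferences should be resisted. Harms are not going unrecorded or untreated: side effects are recorded at Visits 2 to 9, and a subject with an allergic reaction is told to stop the product and seek urgent care. Nothing shows that any event was in fact misreported. No planned efficacy result is affected, and Section 6.3 plans no SAE table. This should be amended, but it does not threaten the trial's main conclusions.

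**What to change.** Four changes, all to wording or classification:

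1. In Section 3.6, define an SAE by the outcome list in the form guidance alone, whether or not the event is expected or related.
2. Keep the three-part rule (unexpected, increased risk, related), including the trend extension, as the test for an unanticipated problem.
3. State that the 5-day IRB report applies to every unanticipated problem and to every SAE that is at least possibly related to the research, listed or not.
4. Reclassify events already logged, blind to arm, before the pharmacy releases assignments at the end of the study (Section 3.6.2).

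Applied to the table above, anaphylaxis in either arm becomes an SAE with a 5-day report. So does a related hospitalization for hypoglycemia or a blood-draw infection, however the word listed is read. The non-serious trend is still reported within 5 days, but as an unanticipated problem and not as an SAE. An unrelated hospitalization is recorded as an SAE without a 5-day report, which keeps the added IRB burden small.

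The cost is a wording amendment and a blind re-reading of logged events. No visit or test is added. The downside is that somewhat more events will be handled as SAEs. A descriptive safety table in Section 6.3 would be a sensible but optional addition and is not part of this point.

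### Answering NO on relatedness when information is lacking takes an unexpected serious event of undetermined relatedness out of the 5-day IRB report

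*Combined protocol and SAP*

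**What the plan says.** Two parts of protocol section 3.6 bear on this.

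**Adverse Events (AEs) and Deviations.** For reporting purposes, the SAE category (and its counterpart for deviations) is drawn narrowly: "defined as unexpected events that increase the risk to subjects and that were possibly, probably, or definitely related to the research". The deadline follows directly: "These must be reported to the WHASC IRB within 5 days". A separate monthly tracking log has a different scope: "Adverse Events (AEs) and Protocol Deviations that do not increase the risks to subjects like those listed in the" (the sentence goes on to name the protocol's list of risks). It goes to study contacts and the site Associate Investigator. An algorithm (section 13, attachment 15) "is attached to assist in guiding the research staff on the categorizing of Adverse Events" and of deviations.

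**Guidance for completing the SAE/AE forms.** Three form questions mirror the three parts of that definition.

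- On expectedness: "Select YES only if the event was NOT already listed in the risks/benefits section of the Protocol or part of an existing disease process".
- On increased risk: "Select YES only if the adverse event was serious, which includes events that are life threatening or results in: death, inpatient hospitalization", with further outcomes listed. A trend in non-serious events that would warrant a protocol change also counts.
- On relatedness, with *possibly* as the lowest of three grades: "Select YES if it is due to the research itself not underlying disease or disorder". A default then covers the case where staff do not have "adequate information available to assess this, the answer would be NO".

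The guidance describes no unknown or pending answer. It does not ask staff to return to a NO that was given for lack of information.

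**The concern.** The form question sets a low bar, because *possibly* related is enough. An event that cannot be assessed has not been shown to fall below that bar, yet the guidance places it there. The answer matters because relatedness is one of three joint conditions for the 5-day report, so a NO given for want of information has the same effect as a NO given on evidence.

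What is at stake is prompt IRB notice of unexpected serious events while their cause is still open. That notice carries weight in this trial. The product is used under an IND (protocol summary, item 8). Section 3.6.1 makes the safety of long-term use an explicit aim. Section 4.9 makes the Principal Investigator responsible for safety monitoring. Research monitors are assigned in section 4.9.5, but no independent data monitoring committee is described.

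**Working it through.** No arithmetic applies. The check applies the form guidance to the three-part SAE definition and then looks for any other rule that would restore the report.

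**Step 1. The condition.** The 5-day report applies if and only if the event is unexpected AND increases risk AND is at least possibly related.

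**Step 2. Four cases under the guidance as written.**

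| Case | Unexpected | Increased risk | Related | 5-day report |
|---|---|---|---|---|
| A. Serious, not a listed risk, not existing disease; judged possibly related | YES | YES | YES | Applies |
| B. Same event; relatedness cannot be assessed | YES | YES | NO (default) | Does not apply |
| C. Same event; judged unrelated on evidence | YES | YES | NO | Does not apply |
| D. Serious, but a listed risk or part of existing disease; relatedness cannot be assessed | NO | YES | NO (default) | Does not apply |

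A and B differ only in the relatedness answer, and in B that answer comes from the default alone. The default therefore changes the reporting result. B and C receive the same answer, so the three answers do not separate an open question from a settled one. In D the event already fails on expectedness, so the default changes nothing.

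**Step 3. Is there another route for case B?**

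- *Monthly log (section 3.6).* It is worded for events that do not increase risk. Case B has increased risk = YES because the event is serious, so the log does not clearly take it. The log is also not addressed to the IRB.
- *Immediate notice to study leads (section 3.6).* This duty attaches to the same defined SAEs, so case B is not clearly covered.
- *Research Monitor (section 3.6).* The monitor completes Section 6 after the site has answered. No power to change the relatedness answer or to start the 5-day report is stated.
- *Reporting of issues (section 4.9.1).* Issues go at once to an investigator, not to the IRB.
- *Monitoring meetings (section 4.9.5).* They verify prompt reporting, including of SAEs, but section 3.6 has already confined that term to events at least possibly related.

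**Result.** Nothing in the available text restores the 5-day report for case B, assigns it a clear alternative, or requires the answer to be reassessed. The conclusion comes from reading the definition and the form guidance together; no single sentence states it.

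**The case against.** The strongest defence is that the relevant material cannot all be seen. The attached algorithm exists to guide categorization and may deal with undetermined events. Section 6 of the form may let the Research Monitor act. Section 4.9.5 commits the trial to ICH GCP and to applicable regulatory requirements. The question includes *possibly*, so an investigator with any basis for suspicion can still answer YES. Staff are told to give as much information as they can, which should keep the default from applying in some cases. The event is still written on a form and seen by investigators.

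Much of this stands as a limit on size. It does not remove the conflict. The text gives the algorithm only an assisting role, and if it said otherwise the written instruction would contradict it. A general commitment to GCP does not tell a coordinator which box to tick when a specific sentence says NO.

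Three stronger readings are tempting, and the documents do not support them.

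- *That every serious event of unknown cause loses its 5-day report.* Listed risks and existing disease already fail on expectedness, and an unknown cause is not the same as relatedness that cannot be assessed.
- *That such events are merely delayed, by up to about a month, through the log.* The log's wording does not take a serious event. The route is undefined, so no length of delay can be given.
- *That the default biases the trial's relatedness data or hides a product signal in the results.* Sections 6.1 and 6.3 plan no analysis of relatedness. Side effects, cardiovascular events and other morbidity are recorded at Visits 2 to 9 whatever their cause, so arms could be compared without the form answer.

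Nor do the documents say how often early reports lack information, so a claim that the default would often decide the answer would be conjecture.

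**Conclusion.** The point holds for a defined class: events that are serious, neither a listed risk nor part of an existing disease, and whose relatedness cannot be assessed when the form is completed. For these, following the guidance exactly takes the event out of the 5-day IRB report and leaves it with no clear route and no reassessment. This is a wrong instruction, not a missing detail, because it contradicts the form's own lowest grade of relatedness.

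The number of such events is not given and cannot be derived. The conclusion assumes that the unseen algorithm and Section 6 contain no overriding rule. If they do, the fault becomes an inconsistency between that rule and the guidance, which still needs correcting. The effect is on IRB oversight, not on any planned efficacy analysis.

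**What to change.** Reconcile the SAE definition and the form guidance in section 3.6. Replace the NO default with wording to this effect: when the relatedness of an unexpected serious event cannot yet be assessed, record it as possibly related, report it to the IRB within 5 days, and update the answer when information arrives.

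An *undetermined* answer would serve as well and avoids forcing a judgement in either direction. In that case the SAE definition must also name undetermined events, or they will still fail the third condition. Check attachment 15 and Section 6 of the form against the new wording.

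The change is one sentence in the guidance, plus a few words in the definition if the *undetermined* answer is used. The price is some expedited reports that are later downgraded; their number cannot be estimated from the documents.
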